3	Death during the study with prior iUPD	Date of the first assessment of iUPD for which death is confirmed at the subsequent assessments.	PFS event
4	Patients still on treatment with no prior iUPD as of data cut-off ^a	Date of the last tumor assessment ^b	Censored
5	Patients still on treatment with prior iUPD as of data cut-off ^a	Date of the first assessment of iUPD for which the data cut-off occurred at the subsequent assessments.	PFS event
6	Treatment discontinuation with no prior iUPD	Date of the last tumor assessment	Censored
7	Treatment discontinuation with prior iUPD	Date of the first assessment of iUPD for which the treatment discontinuation occurred at the subsequent assessments.	PFS event
8	New anticancer treatment started with no prior iUPD	Date of the last tumor assessment before start of new treatment	Censored
9	New anticancer treatment started with prior iUPD	Date of the first assessment of iUPD for which the anticancer treatment started at the subsequent assessments.	PFS event
10	No post baseline tumor assessments	Date of the first dose	Censored
11	No baseline or unreadable baseline assessment but readable post baseline assessments	Date of the first dose	Censored

a. For PFS analysis, the date of last tumor assessment refers to the date of last adequate tumor assessment.
b. This refers to patients who were still receiving study treatment at time of data cutoff.

Table 8. Censoring Rules for Overall Survival (OS)

Situation	End Date	Outcome
Death before cut-off	Date of death	OS event
Death after data cut-off	Date of data cut-off	Censored
Patient still alive at data cut-off	Date of data cut-off	Censored
Patient discontinued treatment due to any reason before data cut-off	Date last known to be alive	Censored

Table 9. Censoring Rules for Duration of Response (DoR) per RECIST 1.1

No.	Situation	End Date	Outcome
1	Documented PD between scheduled visits	Date of the first assessment that determined PD	DoR event
2	Death during the study with no prior PD	Date of death	DoR event
3	Patients still on treatment without PD as of data cut-off ^a	Date of the last tumor assessment ^b	Censored
4	Treatment discontinuation for reasons other than PD or death	Date of the last tumor assessment	Censored
5	New anticancer treatment started	Date of the last tumor assessment before start of new treatment	Censored
6	Death or PD after two or more missed tumor assessments ^c	Date of the last tumor assessment before missed assessments	Censored

- a. For DoR, the date of last tumor assessment refers to the date of last adequate tumor assessment.
- b. This refers to patients who were still receiving study treatment at time of data cutoff.
- c. Two or more missed tumor assessments is defined as having either one of the following two durations being longer than 77 days (= (21 [days/cycle] x 3 [cycles] + 7 [days]) x 2):
 - Duration between two consecutive tumor assessments
 - Duration between the last tumor assessment and death or PD

Table 10. Censoring Rules for Duration of Response (DoR) per iRECIST

No.	Situation	End Date	Outcome
1	Documented iCPD between scheduled visits	Date of the first assessment of iUPD for which iCPD is confirmed at the subsequent assessments.	DoR event
2	Death during the study with no prior iUPD and no prior iCPD	Date of death	DoR event
3	Death during the study with prior iUPD	Date of the first assessment of iUPD at which death is confirmed at the subsequent assessments.	DoR event
4	Patients still on treatment with no prior iUPD as of data cut-off ^a	Date of the last tumor assessment ^b	Censored
5	Patients still on treatment with prior iUPD as of data cut-off ^a	Date of the first assessment of iUPD for which the data cut-off occurred during the subsequent assessments.	DoR event
6	Treatment discontinuation with no prior iUPD	Date of the last tumor assessment	Censored
7	Treatment discontinuation with prior iUPD	Date of the first assessment of iUPD for which the treatment discontinuation occurred during the subsequent assessments.	DoR event
8	New anticancer treatment started with no prior iUPD	Date of the last tumor assessment before start of new treatment	Censored
9	New anticancer treatment started with prior iUPD	Date of the first assessment of iUPD for which the anticancer treatment started at the subsequent assessments.	DoR event

- a. For DoR, the date of last tumor assessment refers to the date of last adequate tumor assessment.
- b. This refers to patients who were still receiving study treatment at time of data cutoff.

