3.2.4. Survival Follow-up

Once disease progression is confirmed or new anticancer therapy is initiated, whichever occurs first, the survival follow-up period begins. During this period, the patient or family should be contacted for survival follow-up every 12 weeks (± 2 weeks) until patient withdraws consent or the study is terminated early by the Sponsor. In addition, all subsequent anticancer treatments will be recorded.

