11.5.3.2. Secondary Efficacy Analyses

ORR and DCR per RECIST 1.1 and iRECIST will be estimated with the exact 2-sided 95% CI. Only the evaluations before disease progression or initiation of new anticancer treatment will be used for the estimation.

DOR per RECIST 1.1 and iRECIST will be estimated only in patients with an objective response of CR or PR. Patients who are alive and progression-free as of the analysis cut-off date will be censored at their last evaluable tumor response assessment prior to initiation of any new anticancer treatment. Patients who start subsequent anticancer therapy without a prior reported

progression will be censored at the last tumor assessments prior to initiation of the subsequent anticancer therapy.

PFS per RECIST 1.1 and iRECIST will be estimated using the Kaplan-Meier method. Patients who die without a reported disease progression will be considered to have progressed on the date of their death. Patients who did not progress or die will be censored on the date of their last tumor assessment. Patients who did not have any on-study assessments and did not die will be censored on the first dosing date. Patients who started any subsequent anticancer therapy without a prior reported progression will be censored at the last tumor assessment prior to initiation of the subsequent anticancer therapy.

Overall survival will be estimated the same as PFS. In the absence of death confirmation or for patients alive as of the OS cut-off date, survival time will be censored at the date of the last known alive date.

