5.4.1. Primary Efficacy Analyses

The primary endpoint is ORR per RECIST 1.1. The description of each efficacy endpoint is provided in Table 3. Tumor assessments will be performed as per Table 1. The evaluation of endpoints will be based on the Investigator or local radiologist.

Table 3. Efficacy Endpoint Definitions

Endpoint	Definition
ORR	The proportion of patients experiencing a best overall response of PR or CR
DCR	the proportion of patients experiencing a best overall response of SD, PR, or CR
DoR	The time from the first documentation of response (CR or PR) to the first documentation of objective tumor progression or death due to any cause, whichever occurs first
PFS	The time from first dose of study therapy to the date of death (any cause) or disease progression, whichever occurs first
OS	The time from the date of first dose to the death date

Abbreviations: ORR=objective response rate; CR=complete response; PR=partial response; SD=stable disease; DCR=disease control rate; DoR=duration of response; OS=overall survival; PFS=progression-free survival

ORR per RECIST 1.1 will be summarized by a binomial response rate for each cohort. ORR per RECIST 1.1 will be calculated based on the best overall response recorded from the start of treatment until progression disease or start of subsequent new anticancer treatment. The overall

response can be derived based on target lesion response, non-target lesion response and the emergence of new lesion for patients with measurable disease at baseline. Table 4 presents the rules to derive the overall response.

The best overall response, CR and PR, will be confirmed with at least 4 weeks intervals of two consecutive time points. A minimum of 6-week interval between initial treatment (first dosing date) and tumor measurement is required for SD. The confirmation rule of the best overall response per RECIST 1.1 is shown in Table 5.

The exact 2-sided 90% CI based on Clopper–Pearson methodology will be derived for ORR.

For Cohort A, the null hypothesis (ORR of 35%) will be rejected if at least 12 responders observed out of 20 patients.

For Cohort B, the null hypothesis (ORR of 25%) will be rejected if at least 9 responders observed out of 20 patients.

Table 4. Overall Response Assessment with Target/Non-target Lesion and New Lesions

Target Lesions	Non-target Lesions	New Lesions	Overall Response
CR	CR	No	CR
CR	Non-CR/Non-PD or Not all evaluated	No	PR
PR	Non-PD or Not all evaluated	No	PR

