5.4.2. Secondary Efficacy Analyses

The secondary efficacy endpoints are ORR per iRECIST, DCR per RECIST 1.1, DCR per iRECIST, DoR per RECIST 1.1, DoR per iRECIST, PFS per RECIST 1.1, PFS per iRECIST, and OS. The description of each efficacy endpoint is provided in Table 3. Tumor assessments will be performed as per Table 1. The evaluation of endpoints will be based on the Investigator or local radiologist.

ORR per RECIST 1.1, ORR per iRECIST, DCR per RECIST 1.1, and DCR per iRECIST will be calculated based on the best overall response. The exact 2-sided 95% CI based on Clopper–Pearson methodology will be derived for DCR. The 95% CI of ORR will also be calculated conventionally.

PFS per RECIST 1.1 and OS will be analyzed using Kaplan–Meier product-limit estimates for each cohort. Patients who are alive and progression-free as of the data cut-off date will be censored at their last evaluable tumor response assessment prior to initiation of any new anticancer treatment. Patients who start subsequent anticancer therapy without a prior reported progression will be censored at the last tumor assessments prior to initiation of the subsequent anticancer therapy. Median PFS per RECIST and OS will be presented with 2-sided 95% CI if estimable. The cumulative PFS and OS will be plotted over time by cohort. The censoring rule for PFS per RECIST and OS is in Table 6 and Table 8, respectively.

PFS per iRECIST will be analyzed using Kaplan–Meier product-limit estimates for each cohort. Patients who are alive and progression-free as of the data cut-off date will be censored at their last evaluable tumor response assessment prior to initiation of any new anticancer treatment. Patients who start subsequent anticancer therapy without a prior reported progression will be censored at the last tumor assessments prior to initiation of the subsequent anticancer therapy. Median PFS per iRECIST will be presented with 2-sided 95% CI if estimable. The cumulative PFS per iRECIST will be plotted over time by cohort.

- The event date to be used for PFS per iRECIST is the first date of iUPD at which iCPD is confirmed at the next assessment.
- If iUPD occurs, but is disregarded because of later iSD, iPR, or iCR, that the iUPD date is not be used as the progression event date.

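### SAP Table 8 contradicts the protocol and itself on overall survival censoring: a survivor off treatment gets two censoring dates, and a death after discontinuation fits both an event row and a censored row.

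*SAP*

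**What the plan says.** OS is defined in SAP Table 3 as "The time from the date of first dose to the death date". SAP 5.4.2, Table 8, then has four rows:

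1. Death before cut-off: OS event at the date of death.
2. Death after cut-off: censored at the cut-off date.
3. "Patient still alive at data cut-off": censored at the cut-off date.
4. "Patient discontinued treatment due to any reason before data cut-off": censored, with end date "Date last known to be alive".

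Protocol 11.5.3.2, repeated in the synopsis, has a single censoring rule. "In the absence of death confirmation or for patients alive as of the OS cut-off date", it says, "survival time will be censored at the date of the last known alive date".

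The SAP 5.4.2 paragraph on PFS per RECIST 1.1 and OS together also states: "Patients who start subsequent anticancer therapy without a prior reported progression will be censored at the last tumor assessments prior to initiation" of that therapy. It does not limit this to PFS, although the paragraph ends by pointing to Table 6 for PFS and Table 8 for OS. SAP Section 8 declares no changes to the planned analyses.

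On follow-up, protocol 3.2.4 says "the patient or family should be contacted for survival follow-up every 12 weeks", with a window of 2 weeks either way. On-treatment cycles are 21 days. Neither document describes a survival-status check at the data cut-off.

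**The concern.** A censoring table should give each patient exactly one date and one status. Table 8 does not, and for living patients it departs from the protocol without saying so. Two programmers could each follow the SAP and produce different OS curves.

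The overlap is not rare. SAP 4.4 triggers the final analysis for the primary objective when all patients are off treatment or have at least 6 months of follow-up, so many patients will be off treatment by then. Disease progression is a reason to stop treatment, so many deaths should also follow discontinuation.

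The choice of date can also matter numerically. Censoring at cut-off keeps a patient in the risk set between the last contact and the cut-off. If a death in that gap has not been reported, the patient counts as a survivor over time that nobody observed.

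**Working it through.** **1. The rules side by side**

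| Patient | Protocol 11.5.3.2 | SAP Table 8 |
|---|---|---|
| Alive at cut-off, on treatment | Last known alive | Cut-off date (row 3) |
| Alive at cut-off, off treatment | Last known alive | Cut-off date (row 3) and last known alive (row 4) |
| Stopped treatment, died before cut-off | Event, by the OS definition | Event (row 1) and censored (row 4) |
| Died on the cut-off date | Event, by the OS definition | No row: the death rows say only before and after |

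Tables 6 and 9 limit their discontinuation rows to reasons other than PD or death. Row 4 of Table 8 has no such limit and does not require the patient to be alive.

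**2. Why the date can matter**

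The Kaplan-Meier estimate is S(t) = ∏(1 − dᵢ/nᵢ), with dᵢ deaths among nᵢ at risk.
- Cut-off censoring keeps patients in nᵢ up to the cut-off. If deaths since the last contact are missing from dᵢ, S(t) is too high.
- Last-known-alive censoring removes living patients from nᵢ after their last contact. If deaths in that same interval are nevertheless known and counted, S(t) is too low.

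**3. Size**

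The documents give no expected OS, OS event count or accrual period, so there is no planned OS figure to reproduce. Everything below rests on assumptions: exponential OS, uniform 12-month accrual, and a cut-off 6 or 12 months after last entry. True 12-month OS is 0.5^(12/median): 43.5%, 50.0%, 57.4% and 66.0% for medians of 10, 12, 15 and 20 months.

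*(a) Contacts every 3 weeks on treatment and every 12 weeks afterwards; median 5 months on treatment; true median OS 12 months.*

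| Rule and knowledge of deaths | Cut-off after last entry | Median (months) | 12-month OS |
|---|---|---|---|
| Row 3 for everyone; deaths known only at contacts | 6 months | 13.1 | 52.5% |
| Row 3 on treatment, row 4 off treatment; deaths known only at contacts | 6 months | 12.1 | 50.2% |
| Row 3 for everyone; all deaths known | 6 months | 12.0 | 50.0% |
| Last known alive; all deaths known, survivors not re-contacted | 6 months | 11.3 | 47.5% |
| Row 3 for everyone; deaths known only at contacts | 12 months | 12.1 | 50.3% |

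The upward shift in the first line is 52.5 − 50.0 = 2.5 points. The downward shift in the fourth is 50.0 − 47.5 = 2.5 points.

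*(b) One contact gap for all patients, row 3 for everyone, deaths known only at contacts.*
- Cut-off 6 months after last entry, gaps of 12 to 14 weeks: the rise in 12-month OS runs from 68.4 − 66.0 = 2.4 points (median 20, 12 weeks) to 47.8 − 43.5 = 4.3 points (median 10, 14 weeks).
- At a true median of 10 months with 12-week gaps, cut-off censoring gives 10.9 months and 47.1%. Last-known-alive censoring gives 10.0 months and 43.6%.
- Cut-off 12 months after last entry: 12-month OS rises by at most about 0.5 points. The median is unchanged for a true median of 10 months and rises by about 0.7 to 0.8 months for 15. For 20 it is not reached.
- Gaps of 3 weeks throughout: 12-month OS rises by at most about 0.8 points.

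**4. Scale against sampling error**

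Take 23 patients per cohort, the middle of the planned 20 to 26, and a true 12-month OS of 50%. The 95% sampling range is at least 50 ± 1.96 × √(0.5 × 0.5/23) × 100 = 50 ± 20.4 points, before any loss to censoring.

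**The case against.** The strongest reply is that this is an editorial gap with little numerical effect. Long contact gaps arise mainly off treatment, and row 4 already gives off-treatment patients the protocol's date. If row 4 governs them, row 3 covers only patients seen about every 3 weeks, and the bias nearly vanishes (12.1 months and 50.2% above). If row 3 means status confirmed on or after cut-off, the last known alive date capped at cut-off is the cut-off date, and nothing changes. The 6-month cut-off comes from SAP 4.4, which times the primary (ORR) analysis; the SAP sets no separate OS cut-off. Any shift is small beside the sampling error in cohorts of this size.

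All of that stands as a limit on size. A reader might infer that Table 8 makes OS biased upward. The documents do not support that: the direction depends on which row prevails and on which deaths are known at analysis, and neither document settles either.

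Two other strong readings also fail. A reader might infer from row 4 that deaths after discontinuation are to be censored. Row 1 and the OS definition point the other way, and a sensible programmer would count the death. A reader might also infer that starting new therapy censors OS. The sentences concern progression-free patients and prior progression, the paragraph sends OS to Table 8, and Table 8 has no new-therapy row. That is loose drafting, though protocol 11.5.3.2 adds to it by saying OS is estimated in the same way as PFS.

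The reply does not remove the contradiction. Choosing row 4 over row 3, or row 1 over row 4, requires a precedence rule that the SAP does not give. Even with row 4 governing off-treatment patients, row 3 still differs from the protocol unless status is confirmed at cut-off.

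**Conclusion.** Table 8 is wrong as written. It conflicts with the protocol for patients alive at cut-off, its rows overlap on both date and status without precedence, and the departure is not declared. This follows from the text alone and needs no simulation.

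The effect on OS is conditional. If the cut-off row is applied to patients whose status is not confirmed at cut-off, 12-month OS rises by about 2.5 points with a cut-off 6 months after last entry, and by up to about 4 points if 12- to 14-week gaps apply to everyone. With a cut-off 12 months after last entry the rise is at most about 0.5 points. It is near zero if the discontinuation row governs off-treatment patients, and zero if all deaths before cut-off are known. The condition is plausible here: off-treatment contacts are 12 weeks apart, give or take 2, and disease-progression deaths are exempt from 24-hour reporting (protocol 9.4.3). All sizes rest on the assumed OS, accrual, contact pattern and cut-off.

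OS is a secondary, descriptive endpoint with no hypothesis test, and the ORR conclusion is unaffected. The correction should be made, but it does not threaten the primary result.

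**What to change.** Replace Table 8 with two rows:

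1. Death on or before the data cut-off: event at the date of death, regardless of treatment status or later anticancer therapy.
2. All other patients: censored at the last date known alive, capped at the data cut-off date.

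Delete the separate discontinuation row. In SAP 5.4.2, limit the tumour-assessment and new-therapy censoring sentences to PFS.

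State one caveat with the rule. If deaths are fully known but survivors are not re-contacted near the cut-off, last-known-alive censoring is itself biased downward, by about 2.5 points at 12 months in the 6-month scenario. The last-alive date should therefore draw on any contact or record up to or after the cut-off, with the cap then applied.

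This restores the protocol's rule, so SAP Section 8 needs no entry for it. If the sponsor prefers to keep the cut-off date for living patients, Section 8 should declare that departure and the SAP should require status confirmed on or after the cut-off. The recommended change costs SAP wording only.

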5.5. Safety Analyses

Unless otherwise specified, all safety analyses will be performed based on All Treated Population. Tables and figures will be generated by cohort.

5.5.1. Extent of Exposure

5.5.1.1. Administration of Study Drug

The following parameters will be summarized by cohort and study drug:

- Duration of treatment
- Number of cycles treated
- Number of doses received
- Cumulative dose
- Relative dose intensity

Duration of treatment (days) will be calculated as: 1) calculate Date of last dose – Date of first dose + 1 for each treated cycle; 2) sum up across all treated cycles.

Cumulative dose is sum of the doses administered to a subject during the treatment period.

Relative dose intensity will be calculated as cumulative dose (dose received) divided by dose planned (taking the dosing cycle into consideration)

A by-patient listing of dosing of study drug and listing of batch number will be also provided.

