3.2.2. Treatment Period and End of Treatment Visit

Treatment discontinuation may occur for any of the reasons listed in [Section 4.4](#). The treatment period is the time from first dose of study therapy (Day 1) to the date of last dose of study therapy. An end-of-treatment (EOT) visit must be performed within 7 days after the decision is made to discontinue all study therapy; at this visit, every effort should be made to perform the assessments outlined in [Table 1](#). For patients who discontinue at a planned study visit, that visit may be considered the EOT visit if all assessments required at EOT are performed.

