5.1.2. Pembrolizumab

Pembrolizumab is administered as an I.V. infusion of 200 mg on Day 1 of each cycle (that is, every 3 weeks). Treatment continues for a maximum of 35 doses or a maximum duration of 2 years (whichever is earlier), or until the patient meets any of the administration discontinuation criteria (see [Section 4.4](#)).

Pembrolizumab should be administered according to the instructions on the approved product label.

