11.5.2. Study Drug Administration

In the All-Treated Population, the following data will be presented separately for futibatinib and pembrolizumab by each cohort and study drug:

- Administration Status
- The total dose, total duration of administration and the number of administration cycles will be summarized
- Status of administration completion
- The rate of administration completion will be presented by cycle.
- The presence or absence of study discontinuation and reasons for study discontinuation will be tabulated by cycle.
- Dose intensity
- Actual dose intensity and relative dose intensity in each patient will be calculated, and descriptive statistics will be presented.

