3.2. Treatment Assignment and Blinding/Unblinding

After the patient's initial eligibility is established and informed consent has been obtained, futibatinib will be administered orally at a dose of 20 mg daily, and pembrolizumab will be administered as an I.V. infusion of 200 mg on Day 1 of each cycle (that is, every 3 weeks).

This is an open-label, non-randomized study. Blinding/unbinding is not applicable.

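### The SAP's per-cycle formula for duration of treatment makes pembrolizumab's duration in days equal to its number of infusions

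*SAP*

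**What the plan says.** SAP 5.5.1.1 opens its list of exposure parameters with "The following parameters will be summarized by cohort and study drug". The list includes duration of treatment, number of cycles treated and, as a separate item, "Number of doses received". Duration in days is the date of last dose minus "Date of first dose + 1 for each treated cycle; 2) sum up across all treated cycles". There is one formula for both drugs, and no other section of the SAP or protocol gives a rule specific to pembrolizumab.

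The schedule is the same in both documents. Protocol 5.1.2 states: "Pembrolizumab is administered as an I.V. infusion of 200 mg on Day 1 of each cycle". SAP 3.2 repeats this, and SAP 3.1 sets the cycle at 21 days. Futibatinib is taken daily.

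Protocol 11.5.2 requires data "presented separately for futibatinib and pembrolizumab by each cohort and study drug", including: "The total dose, total duration of administration and the number of administration cycles will be summarized". It gives no formula. Protocol 4.4 and 5.1.2 limit pembrolizumab to 35 doses or 2 years, whichever comes first. Protocol 3.2.2 says: "The treatment period is the time from first dose of study therapy (Day 1) to the date of last dose of study therapy".

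**The concern.** Taking last minus first dose date inside each cycle works for a drug taken every day of the cycle. For a drug given once per cycle it removes the whole interval between doses and leaves a count of dosing days. The pembrolizumab row would be labelled as duration in days but would hold the number of infusions, repeating another row of the same table.

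At stake is whether the report states how long patients were on pembrolizumab. In a combination study a reader will compare exposure to the two drugs side by side. Under this rule a patient with 10 undelayed cycles of both drugs shows 210 days of futibatinib and 10 days of pembrolizumab. Because the figure ignores delays, it also cannot separate a patient treated on schedule from one whose infusions were repeatedly postponed.

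**Working it through.** The documents state no duration figure to reproduce, so the check applies the SAP formula to the planned schedule.

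**Inputs**
- Duration rule, applied by study drug: SAP 5.5.1.1.
- Pembrolizumab: one infusion, on Day 1 of each cycle (Protocol 5.1.2, SAP 3.2).
- Cycle length: 21 days (SAP 3.1).
- Maximum of 35 pembrolizumab doses (Protocol 4.4 and 5.1.2).

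**Formulas for c infusions, 21 days apart**
- SAP rule: each cycle gives 0 + 1 = 1 day, so the total is c.
- First to last infusion, inclusive: 21(c - 1) + 1.
- With the last 21-day interval counted: 21(c - 1) + 21 = 21c.
- Shortfall against first-to-last: 21(c - 1) + 1 - c = 20(c - 1).

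| Infusions | SAP rule (days) | First to last (days) | With last interval (days) | Shortfall vs first-to-last (days) | First-to-last / SAP |
|---|---|---|---|---|---|
| 1 | 1 | 1 | 21 | 0 | 1 |
| 2 | 2 | 22 | 42 | 20 | 11 |
| 4 | 4 | 64 | 84 | 60 | 16 |
| 10 | 10 | 190 | 210 | 180 | 19 |
| 35 | 35 | 715 | 735 | 680 | 20.4 |

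In the last row, 35 x 21 = 735 days is close to the 2-year limit that the protocol sets beside the 35-dose limit (2 x 365.25 = 730.5 days). The SAP rule reports that same course as 35 days.

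**Delay.** Take four infusions with a 14-day delay before the fourth, on days 1, 22, 43 and 78. The SAP rule still gives 4 days. First to last is 78 - 1 + 1 = 78 days, or 77 + 21 = 98 with the last interval.

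**Futibatinib for comparison.** Uninterrupted daily dosing gives 21 days per cycle under the SAP rule, so 10 cycles give 210 days, the same as first dose to last dose.

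**Does the equality always hold?** A cycle without pembrolizumab adds 0 days and 0 doses. An infusion stopped and restarted on the same date still adds 1 day. Only an infusion continued on a later date within the same cycle would break the equality, and the schedule does not plan for that.

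**The case against.** The best case for leaving the text alone is that little depends on it. No decision rule uses the row. The same list gives cycles treated and doses received, and a by-patient dosing listing is planned, so an alert reader would see that 10 days against 10 cycles is not time on treatment and could recover the dates. This stands as an argument about severity. It does not make the row correct.

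Another defence is that dose dates might be pooled across the two drugs within a cycle. The SAP summarizes by study drug and Protocol 11.5.2 asks for each drug separately, so pooling would not follow the text.

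A reader might infer more than the documents support, in four ways:
- **A direct conflict with Protocol 3.2.2.** That section defines the treatment period for study therapy as a whole, not a per-drug exposure formula. It supports the calendar span only by analogy. The firmer support is Protocol 11.5.2, together with the 35-dose or 2-year limit, which treats pembrolizumab duration as calendar time.
- **A faulty rule for futibatinib.** No error is shown there. Summing within cycles and leaving out off-drug gaps between cycles is a legitimate convention for a daily drug.
- **Distorted adverse event rates.** SAP 5.5.2.7 divides by a total exposure time but does not link it to this row.
- **An effect on relative dose intensity.** SAP 5.5.1.1 says only that the planned dose takes the dosing cycle into account. Whether duration enters is not stated, so an effect is neither shown nor excluded.

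**Conclusion.** Followed exactly, SAP 5.5.1.1 gives a pembrolizumab duration equal to the infusion count and does not deliver the per-drug duration that Protocol 11.5.2 requires. On an undelayed schedule the row is short of the first-to-last span by 20 x (c - 1) days: nothing at one infusion, 180 days at 10 and 680 at 35. The protocol does not say whether the final dosing interval counts; if it does, the reference values are 210 and 735 days rather than 190 and 715, and the conclusion is the same.

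The conclusion rests on the formula being applied to each drug's own dose dates and on one infusion date per cycle, both of which are the plain reading. The error is limited to one descriptive row for one drug, so the severity is minor.

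**What to change.** In SAP 5.5.1.1 add a rule for pembrolizumab: duration of treatment (days) = date of last infusion - date of first infusion + 1, taken over the whole of that patient's pembrolizumab treatment. As an option, use + 21 instead of + 1 to include the final dosing interval, truncated at death or data cut-off. State the choice in the table footnote.

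The per-cycle rule for futibatinib may stay. If it does, the footnote should say that futibatinib duration leaves out off-drug gaps between cycles and pembrolizumab duration includes them. No change to SAP 5.5.2.7 is needed.

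At 10 undelayed cycles the table would then show 210 days of futibatinib and 190 of pembrolizumab, or 210 and 210 with the option. In the four-infusion delay example pembrolizumab would show 78 days (98 with the option) instead of 4.

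The cost is one SAP sentence, a footnote and minor programming from dosing dates already collected. The one drawback is that the two drugs' durations follow slightly different conventions, which the footnote discloses.
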